16.2.7 Follow-up of All Adverse Events/Serious Adverse Events

The clinical course of each adverse event should be followed until resolution, stabilization, or until it has been determined that the study treatment or participation is not the cause. Serious adverse events that are still ongoing at the end of the study period must be followed to

determine the final outcome. The Investigator must provide the Sponsor with all relevant follow-up information necessary to facilitate a thorough understanding of the event and judgment regarding the relationship to the study drug or placebo. Subjects who discontinue because of an adverse event before completing the study (Week 52) will be evaluated immediately and contacted 13 weeks (± 3 days) after their last injection of study drug to determine if the adverse event has resolved, continues unabated, or has reached a new baseline.

16.2.8 Adverse Event Reporting

16.2.8.1 Adverse Events Requiring Expedited Reporting

The following events should be forwarded to the Sponsor within 24 hours of becoming aware of the event:

- All SAEs, regardless of causality;
- Overdose (with or without an adverse event);
- Inadvertent or accidental exposure;
- All adverse events of special interest (see Section 16.2.4);
- Pregnancy (see Section 16.2.5); and
- Unexpected therapeutic benefit.

16.2.8.2 Timeframe for Collecting and Reporting Serious Adverse Events, Adverse Events of Special Interest, and Other Immediately Reportable Adverse Events

Serious adverse events, adverse events of special interest, and other immediately reportable adverse events occurring during the study period (or within 13 weeks ± 3 days of last study drug injection for subjects discontinuing participation prematurely) must be reported via telephone to the Medical Monitor or designee and then followed up using the appropriate Adverse Event Form, **within 24 hours** of the time any study staff member is made aware of the event. Additional eCRF and/or paper documentation may need to be supplied to the Sponsor (or designee).

You must also report any SAE of which you become aware that occurred within 13 weeks after the last dose of study drug (regardless of relationship to study drug). Any SAEs (at least possibly related to study drug) that you become aware of after 13 weeks after the last dose of study drug should also be reported to the Sponsor (or designee). These post-study events should be reported to the Sponsor using MedWatch Forms

When reporting adverse events of special interest, study staff should provide copies of supporting documentation described in Section 16.2.4. Please note that the supporting documentation provided must be redacted to remove any subject identifiers other than the study subject identification number and subject's initials.

16.3 Vital Signs

Resting vital signs (blood pressure, pulse, respiratory rate, and temperature) will be measured after sitting quietly for at least 5 minutes at screening and each study visit or, if applicable, at discontinuation from the study.

16.4 Clinical Laboratory Evaluations

16.4.1 Standard Laboratory Tests

Safety blood and urine specimens (fasting) (see Table 3) will be collected from all subjects at screening and Weeks 13, 26, and 52 or, if applicable, at discontinuation from the study. Clinical laboratory testing will also be performed as needed at the Investigator's discretion throughout the study. For this multicenter study, a central laboratory (TBD) will be used that is directly accredited by the College of American Pathologists (CAP) and licensed by the Clinical Laboratory Improvement Act of 1988 (CLIA); both certification and accreditation must be renewed every 2 years. The laboratory will need to provide a copy of current certification and provide the Laboratory Normals for their laboratory values to determine the upper limit of normal (ULN).

Table 3. Hematology, Chemistry and Urinalysis Tests

Hematology	Chemistry	Urinalysis
Hemoglobin	Cholesterol	Specific gravity
Hematocrit	Phosphorus	pH
Platelet count	Sodium	Glucose
Red blood cell count	Potassium	Blood
MCV	Calcium	Protein
MCH	Urea nitrogen	Color
MCHC	Creatinine	Nitrites
WBC count	Albumin	Ketones
WBC differential (%)	Total protein	Bilirubin
bands	Aspartate aminotransferase	Urobilinogen
neutrophils	Alanine aminotransferase	Leukocyte esterase
lymphocytes	Alkaline phosphatase	
monocytes	Gamma-glutamyl transferase	
eosinophils	Uric acid	
basophils	Total bilirubin	
	Glucose	
	Lactate dehydrogenase	

Abbreviations: MCH = mean corpuscular hemoglobin, MCHC = mean corpuscular hemoglobin concentration, MCV = mean corpuscular volume, WBC = white blood cell

16.4.2 Pregnancy Test

A "dip-stick" urine pregnancy test will be performed for all female subjects of childbearing potential at screening, on Day 1 (before the first injection of study drug), as needed at the Investigator's discretion throughout the study, and at Week 52 or, if applicable, at discontinuation from the study. Sites are encouraged to use any FDA-approved urine pregnancy test.

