Effectiveness Endpoints	
 • Unstimulated salivary flow rate (USFR) (Assessor) at each study visit; • Clinical Global Impression of Severity (CGI-S) and Change (CGI-C) (Assessor) at each study visit; • DFSS-I (Assessor) at each study visit; • DFSS-S as assessed via subject's diary at each assessment time point; • Patient Global Impression of Severity (PGI-S) and Change (PGI-S) at each study visit; and • Drooling Impact Score (DIS) (Subject) at each study visit.
Duration	
The planned duration of participation for each subject is a minimum of 26 weeks and a maximum of 52 weeks (excluding up to a 21-day screening period), including:
 
 • Up to four 13-week (± 2 weeks) treatment sessions over a 1-year period. Note that Treatment Sessions 3 and 4 are likely, but may not be necessary as the study progresses because the study may be stopped early once enough subjects have completed the study to meet FDA safety database requirements. Any subject that enters the study, however, is required to participate at least through 6 months (i.e., complete Treatment Sessions 1 and 2).
Study Visits	
Screening Period: up to 21 days
 
Treatment Session 1
 
Day 1 (day of injection of study drug) and 4 weeks (± 3 days), 8 weeks (± 3 days), and 13 weeks (± 2 weeks) post-injection, and a telephone follow up 24 hours (± 1 day) post-injection.
 
Treatment Sessions 2, 3, and 4
 
For each 13-week treatment session:

	
 • 4 weeks (± 5 days) and 13 weeks (± 2 weeks) after each treatment, with a telephone follow up 1 week (± 1 day) and 8 weeks (± 5 days) after each treatment. Note that the last visit of a prior treatment session will serve as the first day of the next treatment session.

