During the screening period, the following will be assessed to evaluate the subject's eligibility to participate in the study: inclusion and exclusion criteria; medical, surgical, and medication history; presence or prior history of aspiration, aspiration pneumonia, choking, and/or dysphagia; complete physical exam (including vital signs, height, and weight); neurologic exam; dental exam; clinical laboratory testing; urine pregnancy testing (females of childbearing potential only); and forced vital capacity (FVC) (if warranted, such as in ALS patients). All subjects successfully completing screening will have the following procedures/assessments conducted at baseline (Day 1) before the first injection of MYOBLOC: brief physical exam (including vital signs); FVC (if warranted); neurologic exam; Columbia Suicide Severity Rate Scale (C-SSRS); oral exam; saliva production quantitatively determined via USFR; qualitative assessments by the Investigator including CGI-S and DFSS-I; subject assessments including PGI-S, DFSS, DIS; and urine pregnancy test (result must be negative to proceed with the injection). Those subjects who satisfy all eligibility criteria may receive a dose of MYOBLOC (3,500 Units) via injections into the submandibular and parotid glands on Day 1. Subjects will be contacted by telephone 24 hours post-injection to inquire about their health status.

Subsequent study visits will occur at Weeks 4 (± 3 days), 8 (± 3 days), 13 (± 2 weeks), 17 (± 5 days), 26 (± 2 weeks), 30 (± 5 days), 39 (± 2 weeks), 43 (± 5 days), and 52 (± 2 weeks), with safety and effectiveness assessments made as detailed in the Schedule of Assessments in Table 2 in Section 14.1; telephone follow up will be done at Weeks 14 (± 1 day), 21 (± 5 days), 27 (± 1 day), 34 (± 5 days), 40 (± 1 day), and 47 (± 5 days)

Injections at each treatment session will be done when the subject returns to baseline status as determined by the Principal Investigator, with a minimum interval of 11 weeks from the prior injection but no later than 15 weeks from the prior injection. If after the first treatment of 3,500 Units the subject develops intolerable side effects, but still wishes to remain in the

study, the Investigator has the discretion to decrease subsequent doses, but to no less than a total dose of 2,500 Units.

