14.2 Screening

Subjects who provide written consent to participate and HIPAA authorization to use their personal health information will be screened for inclusion in the study. A screening window of up to 21 days is provided to ensure the Investigator has adequate time to evaluate the subject's medical/surgical history, screening laboratory tests, and other eligibility criteria.

The following activities will be completed:

- Review of inclusion and exclusion criteria;
- Demographics; medical/surgical/medication history; and baseline history of aspiration, aspiration pneumonia, choking, and dysphagia;
- Salivary flow rate collection (USFR);
- DFSS-I;
- Complete physical examination (including vital signs, height, and weight);
- Neurologic exam;
- Dental exam by a licensed dentist (DDS or DMD), including 4 bite-wing radiographs or panoramic imaging (if edentulous or if bite-wing x-rays are difficult due to limited teeth);
- Dental questionnaire by subject or caregiver;
- Screening laboratory tests (full chemistry panel including glucose and alkaline phosphatase; hematology; urinalysis) in fasting state;
- Urine pregnancy test (females of childbearing potential only); and
- Respiratory function including FVC in all subjects with ALS, and in other subjects if warranted at the discretion of the Investigator.

Subjects will be advised to contact study staff if they require ANY new medication so the Investigator can be consulted on the potential impact to the subject's eligibility in the study (see Section 16.10).

14.3 Treatment Session 1

14.3.1 Day 1

Subjects who are deemed eligible for treatment based on screening assessments/procedures will have the assessments listed below completed on Day 1 (baseline) before injection of MYOBLOC.

- Evaluation of adverse events;
- Brief physical exam (including vital signs and weight);

- FVC in all subjects with ALS, and other subjects if done at screening;
- Neurologic exam;
- Oral exam by the Investigator;
- Columbia Suicide Severity Rating Scale (C-SSRS) Baseline version;
- Urine pregnancy test (females of childbearing potential only, performed just before injection of study drug). Result must be negative to proceed with the injection;
- CGI-S (Assessor) before USFR;
- Saliva production quantitatively determined via USFR collection;
- DFSS-I;
- PGI-S (Subject);
- DIS (Subject); and

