- DFSS-S – site personnel will teach the subject how to use the subject diary to complete the DFSS and the subject will perform a practice entry at this visit, with the first real entry to occur that evening.

Once all assessments have been completed, evaluated, and eligibility confirmed, the subject will receive a dose of MYOBLOC via injections into the submandibular and parotid glands as detailed in Section 13.2. Subjects will be contacted by telephone 24 hours (± 1 day) post-injection to inquire about their health status and to remind the subject to complete their diary.

14.3.2 Weeks 4, 8, and 13

Subjects will return to the clinic for follow-up assessments/procedures at Weeks 4, 8, and 13. Visit windows are provided to allow flexibility in scheduling subjects for appointments: Weeks 4 and 8 have a ± 3 day window and Week 13 has a ± 2 week window. The following assessments will be completed at each study visit unless otherwise specified:

- Complete (Weeks 4 and 13) and brief (Week 8) physical exam (including vital signs and weight);
- FVC in all subjects with ALS, and other subjects if done at screening, at Weeks 4 and 13 and as needed, per Investigator discretion, at Week 8;
- Clinical laboratory tests (fasting), including full chemistry panel (including glucose and alkaline phosphatase), hematology, and urinalysis at Week 13 and as needed, per Investigator discretion, at Weeks 4 and 8;
- Urine pregnancy test (as clinically warranted);
- Neurologic exam at Week 13 and as clinically warranted at Weeks 4 and 8;

- Dental exam by a licensed dentist at Weeks 4 and 13, and as clinically warranted based on predefined safety criteria;
- Oral exam by Investigator (Week 8);
- Evaluation of adverse events;
- C-SSRS Since Last Visit version;
- Review of concomitant medications;
- Review of subject diary;
- CGI-S and CGI-C (Assessor) before USFR;
- USFR collection;
- DFSS-I;
- PGI-S and PGI-C (Subject);
- DIS (Subject); and
- DFSS-S via entry in the subject's diary, not during study visit, daily for first 2 weeks after injection of MYOBLOC and then weekly for remainder of treatment session.

14.4 Treatment Session 2

14.4.1 Day 1

On Day 1 of treatment session 2 (same day as Week 13 visit), subjects may receive MYOBLOC (as detailed in Section 13.2) after all 13-week assessments have been completed for the prior treatment session.

14.4.2 Weeks 14, 17, 21, and 26

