A telephone follow up will be made 1 week (± 1 day) after injection of MYOBLOC (Week 14) and at Week 21 (± 5 days) to inquire about subjects' health status and to assess adverse events and review concomitant medications (see Section 16.10). Subjects will return to the clinic at Week 17 (± 5 days) and Week 26 (± 2 weeks) and the assessments listed below will be completed at each visit, unless otherwise specified. Note that the Week 26 visit will serve as the Day 1 visit for the subsequent injection of MYOBLOC (see Section 14.5.1).

- Evaluation of adverse events;
- Brief (Week 17) and complete (Week 26) physical exam (including vital signs and weight);
- FVC (as clinically warranted);
- Clinical laboratory tests (fasting), including full chemistry panel (including glucose and alkaline phosphatase), hematology, and urinalysis at Week 26 and as needed, per Investigator discretion, at Week 17;
- Urine pregnancy test (as clinically warranted);
- Neurologic exam (as clinically warranted);

- Dental exam by a licensed dentist at Week 26 (including 4 bite-wing radiographs or panoramic imaging [if edentulous or if bite-wing x-rays are difficult due to limited teeth]), and as clinically warranted based on predefined safety criteria;
- Oral exam by Investigator (Week 17);
- C-SSRS Since Last Visit version;
- Review of concomitant medications;
- Review of subject diary;
- CGI-S and CGI-C (Assessor) before USFR;
- USFR collection;
- DFSS-I;
- PGI-S and PGI-C (Subject);
- DIS (Subject); and
- DFSS-S via entry in the subject's diary, not during study visit, daily for first 2 weeks after injection of MYOBLOC and then weekly for remainder of treatment session.

14.5 Treatment Session 3

14.5.1 Day 1

On Day 1 of treatment session 3 (same day as Week 26 visit), subjects may receive MYOBLOC (as detailed in Section 13.2) after all 13-week assessments have been completed for the prior treatment session.

14.5.2 Weeks 27, 30, 34, and 39

A telephone follow up will be made 1 week (± 1 day) after injection of MYOBLOC (Week 27) and at Week 34 (± 5 days) to inquire about subjects' health status and to assess adverse events and review concomitant medications (see Section 16.10). Subjects will return to the clinic at Week 30 (± 5 days) and Week 39 (± 2 weeks) and the assessments listed below will be completed at each visit, unless otherwise specified. Note that the Week 39 visit will serve as the Day 1 visit for the subsequent injection of MYOBLOC (see Section 14.6.1).

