- Evaluation of adverse events;
- Brief (Week 30) and complete (Week 39) physical exam (including vital signs and weight);
- FVC (as clinically warranted);
- Clinical laboratory tests (as clinically warranted);
- Urine pregnancy test (as clinically warranted);
- Neurologic exam (as clinically warranted);
- Dental exam by a licensed dentist (as clinically warranted based on predefined safety criteria);

- Oral exam by Investigator;
- C-SSRS Since Last Visit version;
- Review of concomitant medications;
- Review of subject diary;
- CGI-S and CGI-C (Assessor) before USFR;
- USFR collection;
- DFSS-I;
- PGI-S and PGI-C (Subject);
- DIS (Subject); and
- DFSS-S via entry in the subject's diary, not during study visit, daily for first 2 weeks after injection of MYOBLOC and then weekly for remainder of treatment session.

14.6 Treatment Session 4

14.6.1 Day 1

On Day 1 of treatment session 4 (same day as Week 39 visit), subjects may receive MYOBLOC (as detailed in Section 13.2) after all 13-week assessments have been completed for the prior treatment session.

14.6.2 Weeks 40, 43, 47, and 52

A telephone follow up will be made 1 week (± 1 day) after injection of MYOBLOC (Week 40) and at Week 47 (± 5 days) to inquire about subjects' health status and to assess adverse events and review concomitant medications (see Section 16.10). Subjects will return to the clinic at Week 43 (± 5 days) and Week 52 (± 2 weeks) and the assessments listed below will be completed at each visit, unless otherwise specified.

- Evaluation of adverse events;
- Brief (Week 43) and complete (Week 52) physical exam (including vital signs and weight);
- FVC (as clinically warranted);
- Clinical laboratory tests (fasting), including full chemistry panel (including glucose and alkaline phosphatase), hematology, and urinalysis at Week 52 and as clinically warranted at Week 43;
- Urine pregnancy test at Week 52 and as clinically warranted at Week 43;
- Neurologic exam at Week 52 and as clinically warranted at Week 43;
- Dental exam by a licensed dentist at Week 52 (including 4 bite-wing radiographs or panoramic imaging [if edentulous or if bite-wing x-rays are difficult due to limited teeth]) and as clinically warranted based on predefined safety criteria at Week 43;
- Oral exam by Investigator at Week 43;

- C-SSRS Since Last Visit version;
- Review of concomitant medications;
- Review of subject diary;
- CGI-S and CGI-C (Assessor) before USFR;
- USFR collection;
- DFSS-I;

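### A negative pregnancy test is required before the first injection only; up to 3 of 4 injections can be given without one

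*Protocol*

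**What the plan says.** For women of childbearing potential, Protocol Section 16.4.2 fixes the dip-stick urine test as follows: "at screening, on Day 1 (before the first injection of study drug), as needed at the Investigator's discretion throughout the study, and at Week 52". A subject who leaves early is tested then.

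For the first injection the test is a gate. Section 14.3.1 (Session 1, Day 1) states: "Result must be negative to proceed with the injection". Section 10 states the same condition for the baseline visit.

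For the repeat injections there is no gate:

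- The visit lists covering Weeks 13, 26 and 39 (Sections 14.3.2, 14.4.2 and 14.5.2) each carry the entry "Urine pregnancy test (as clinically warranted" in place of a fixed test.
- Section 14.4.1 says: "On Day 1 of treatment session 2 (same day as Week 13 visit), subjects may receive MYOBLOC". Sections 14.5.1 and 14.6.1 use the same form for the third and fourth injections: "On Day 1 of treatment session 3 (same day as Week 26 visit), subjects may receive MYOBLOC" and "On Day 1 of treatment session 4 (same day as Week 39 visit), subjects may receive MYOBLOC". The only condition each adds is that the assessments closing the previous session are complete.
- Section 13.2 (dosing) holds a repeat injection for persisting moderate to severe dysphagia or dry mouth, but has no pregnancy condition.

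SAP Section 2.6.2 describes the same testing schedule. Pregnancy is exclusion criterion 11 (Section 11.1.2), and Section 16.2.5 requires any subject who becomes pregnant to be withdrawn.

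**The concern.** The protocol treats pregnancy as a bar to dosing, both at entry and whenever it becomes known. Each repeat injection is a new exposure to the same drug, so the reason for testing before injection 1 applies equally to injections 2, 3 and 4. Yet a continuing subject has no required test between Day 1 and Week 52. The Week 52 test comes nominally 52 − 39 = 13 weeks after the last injection, too late to prevent any exposure.

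What is at stake is fetal exposure in a woman whom the protocol would have withdrawn had her pregnancy been known. Estimates, error rates and analysis populations are unaffected. The documents agree with one another on this schedule, so this is a gap in the design and not a contradiction.

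**Working it through.** The plan gives no figure of its own to reproduce. The check compares injection visits with required tests.

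**Inputs**

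- Injections: at most 4, at Day 1 and Weeks 13, 26 and 39 (Protocol Section 13.2; SAP Section 2.2).
- Required tests: screening, Day 1, and Week 52 or discontinuation (Sections 14.7 and 16.4.2).
- Visit window at Weeks 13, 26 and 39: ±2 weeks (Table 2).
- Interval from the prior injection: 11 to 15 weeks (Section 10).
- Routine urine collection: screening and Weeks 13, 26 and 52 (Section 16.4.1).
- Planned enrolment: 120 to 200 (Section 17.2).

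**Step 1: injections against required tests, and the age in weeks of the last required negative result**

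| Injection | Visit | Negative test required? | Nominal | Fixed windows (week ±2) | Timed from prior injection (k × 11 to k × 15) |
|---|---|---|---|---|---|
| 1 | Day 1 | Yes (10, 14.3.1) | same day | same day | same day |
| 2 | Week 13 | No (14.3.2, 14.4.1) | 13 | 11–15 | 11–15 (k = 1) |
| 3 | Week 26 | No (14.4.2, 14.5.1) | 26 | 24–28 | 22–30 (k = 2) |
| 4 | Week 39 | No (14.5.2, 14.6.1) | 39 | 37–41 | 33–45 (k = 3) |

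The Week 13 cell of the pregnancy-test row in Table 2 is blank in the text available for review and may be part of a merged cell. The reading for that visit therefore rests on Section 14.3.2.

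**Step 2: share of injections without a required test**

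- Four sessions: 4 − 1 = 3 of 4.
- Three sessions: 3 − 1 = 2 of 3.
- Sessions 1 and 2 only: 2 − 1 = 1 of 2.

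The shorter cases matter because the Synopsis says: "Note that Treatment Sessions 3 and 4 are likely, but may not be necessary as the study progresses".

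**Step 3: could another provision catch an unrecognised pregnancy before re-injection?**

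- *Contraception (criterion 11).* It lowers the chance of pregnancy but detects nothing. No visit list in Section 14 includes a contraception check.
- *Discretionary testing, and discontinuation of subjects who cease to meet entry criteria (12.3).* Both depend on someone already suspecting pregnancy.
- *Withdrawal on pregnancy (16.2.5) and reporting within 24 hours (16.2.8.1).* Both act only once the pregnancy is known.
- *Mandatory test at early discontinuation (14.7) and at Week 52.* Both follow the subject's last injection.

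None closes the gap.

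**Step 4: burden of closing it**

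The documents do not give the number of women of childbearing potential. Assume 5% to 20% of enrolment.

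- Women: 120 × 0.05 = 6 to 200 × 0.20 = 40.
- All have four injections: 6 × 3 = 18 to 40 × 3 = 120 extra tests.
- All have Sessions 1 and 2 only: 6 × 1 = 6 to 40 × 1 = 40 extra tests.

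Urine is already collected at 2 of the 3 repeat-injection visits (Weeks 13 and 26), so only Week 39 adds a routine collection.

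**The case against.** The strongest reply is that this was a consistent design choice. The protocol has fixed tests at both ends, discretion in between, mandatory contraception for the study and 2 months after, and an office visit before every re-injection. No rule in the documents is broken. The counts above describe the calendar and not a risk: the documents give no pregnancy probability, no estimate of fetal harm and no number of women at risk. Eligibility runs from 18 to 85 years. Parkinson's disease, ALS and stroke are among the named causes, but so are adult cerebral palsy, traumatic brain injury and medication effects, so the share cannot be inferred either way. The sponsor may also have addressed reproductive risk in material not available here, such as the investigator's brochure.

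Much of this stands as a limit on importance. The expected number of cases is probably small, and the recommendation does not rest on a large one. It does not answer the point itself, because every listed safeguard needs a pregnancy to be suspected or known first.

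A second reply is timing. The SAP carries a July 2018 date and already reports in Section 3.4 how far the two analysis populations differ, which suggests that enrolment was finished. If dosing is complete, the change can help only a later study. That affects where the fix can be applied, not whether the schedule had the gap.

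**Conclusion.** The concern holds. A negative test is required before 1 injection only; up to 3 of 4 have none, falling to 2 of 3 or 1 of 2 for subjects with fewer sessions. At the repeat injections the last required negative result is nominally 13, 26 and 39 weeks old, and up to 45 weeks old at the fourth if each injection is given at the end of its interval.

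Confidence in the reading of the schedule is high. The size of the clinical risk cannot be worked out from the documents and is probably small. The change is worth recommending because it is cheap and makes the dosing rule match the exclusion and withdrawal rules. The 5% to 20% share is an assumption and affects only the cost figure.

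**What to change.** In the protocol, for women of childbearing potential:

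1. Make the dip-stick urine test mandatory before the injection at Weeks 13, 26 and 39, whenever one is given (Table 2 and Sections 14.3.2, 14.4.2, 14.5.2 and 16.4.2).
2. Repeat the Day 1 condition, "Result must be negative to proceed with the injection", in Sections 14.4.1, 14.5.1 and 14.6.1.
3. For consistency, carry the condition into Sections 10 and 13.2.

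No SAP analysis changes. The SAP's copy of the schedule (Tables A and B, Section 2.6.2) should be conformed so that the two documents still agree.

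Injections without a required test fall from 3 of 4 to 0 of 4, and the required result is then obtained at the injection visit itself. The cost is at most three dip-sticks per woman, with a test and office visits already in the protocol, plus minor site time. A dip-stick can miss a very early pregnancy, so the change reduces the risk without removing it.
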